8.9.4 Use of Electronic Diaries

At the time of consent, the participants must confirm they will be willing to complete an eDiary using either an application downloaded to their own device or using a device that is provided at the time of enrollment. Before enrollment on Day 1, the participants will be instructed to download the eDiary application or will be provided an eDiary device to record solicited ARs (Section 8.11.3). Participants will also use the eDiary to record any ILI symptoms (as part of active surveillance) that they experience after vaccination from Day 1 through Day 361 (Month 12)/EoS.

Participants will be instructed on Day 1 on thermometer usage to measure body temperature, ruler usage to measure injection site erythema and swelling/induration (hardness), and self-assessment of localized axillary swelling or tenderness on the same side as the injection arm.

Participants will record data into the eDiary starting approximately 30 minutes after injection under supervision of the clinic staff to ensure successful entry of assessments. The clinic staff will perform any retraining as necessary. Participants will continue to record data in the eDiary after they leave the clinic, preferably in the evening and at the same time each day, on the day of injection, and for 6 days following injection.

Participants will record the following data in the eDiary:

- Solicited local and systemic ARs, as defined in Section 8.11.3, that occur on the day of vaccination and during the 7 days after vaccination (ie, the day of injection and 6 subsequent days).
- Symptom reporting of ILI. Participants will be instructed to report via Symptom Reporting eDiary or by contacting the site if ILI symptoms have been experienced from Day 1 to Day 361 (Month 12)/EoS. If symptoms are reported, the investigator must contact the participant to assess symptoms and ensure an NP swab is collected within 72 hours of symptom onset. If possible, NP swabs should be collected prior to initiation of antiviral therapy. If there is no response to an eDiary prompt for 2 consecutive entries, the clinic staff will attempt to contact the participant by telephone call (Section 8.9.2).

- Daily oral body temperature measurement should be performed at approximately the same time each day using the thermometer provided by the clinic. If body temperature is taken more than once in a given day, only the highest temperature reading should be recorded.
- Measurements, as applicable, for solicited local ARs (injection site erythema and swelling/induration) will be performed using the ruler provided by the clinic.
- Any medications taken to treat or prevent pain or fever on the day of injection and for the next 6 days.
- Patient-reported outcome questionnaires, as defined in [Section 8.17](#). All participants will receive eDiary prompts to complete the EQ-5D-5L questionnaire on Day 1, Day 91, Day 181, Day 271, and Day 361 (Month 12)/EoS, and participants who report symptoms of ILI will receive eDiary prompts to complete EQ-5D-5L and WPAI:ILI questionnaires.

The eDiary will be the only source document allowed for solicited systemic or local ARs (including body temperature measurements). Participants will be instructed to complete eDiary entries daily. Quantitative temperature recordings and measurement of any injection site erythema or swelling/induration reported on the following day may be excluded from the analyses of the solicited ARs.

Clinic staff will review eDiary data with participants at a visit 7 days after the injection.

8.9.5 Blood Sampling Volumes

The maximum planned volumes of blood sampled per participant will not exceed 450 mL for the complete study.

8.9.6 Ancillary Supplies for Participant Use

Clinics will distribute Sponsor-provided oral thermometers and rulers for use by participants in assessing body temperature and injection site reactions, for recording solicited ARs in the eDiaries. Based on availability, smartphone devices may be provided to those participants who do not have their own device to use for eDiary activities.

8.10 Clinical Assessments

Participants who develop symptoms consistent with protocol-defined ILI ([Section 8.11.5](#)) and/or COVID-19 will have NP swabs collected for testing. The initial test will be a real-time, RT-PCR-based assay, to determine if either influenza A and/or B strains, as well as other respiratory viruses such as SARS-CoV-2, are present in the clinical sample. For samples that test positive for influenza in the RT-PCR assay, further testing by PCR-based genetic sequencing of the HA segments and/or other influenza virus genes may be performed to identify the specific subtype of the influenza strain. The RT-PCR positive samples may be cultured. Cultured viruses may be used to evaluate similarity (match) to the current year's vaccine strains using ferret

antisera to determine antigenic similarity to vaccine strains. See [Section 8.11.5](#) for how to capture these illnesses.

8.11.2 Serious Adverse Events

An AE (including an AR) is considered an SAE if, in the view of either the investigator or Sponsor, it results in any of the following outcomes:

- **Death**
A death that occurs during the study or that comes to the attention of the investigator

during the protocol-defined follow-up period must be reported to the Sponsor, whether or not it is considered related to IP.

- **Is life-threatening**

An AE is considered life-threatening if, in the view of either the investigator or the Sponsor, its occurrence places the participant at immediate risk of death. It does not include an AE that, had it occurred in a more severe form, might have caused death.

- **Inpatient hospitalization or prolongation of existing hospitalization**

In general, inpatient hospitalization indicates the participant was admitted to the hospital or emergency ward for at least one overnight stay for observation and/or treatment that would not have been appropriate in the physician's office or outpatient setting. The hospital or emergency ward admission should be considered an SAE regardless of whether opinions differ as to the necessity of the admission. Complications that occur during inpatient hospitalization will be recorded as an AE; however, if a complication/AE prolongs hospitalization or otherwise fulfills SAE criteria, the complication/AE will be recorded as a separate SAE.

- **Persistent or significant incapacity or substantial disruption of the ability to conduct normal life functions**

This definition is not intended to include experiences of relatively minor medical significance such as uncomplicated headache, nausea/vomiting, diarrhea, influenza, and accidental trauma (eg, sprained ankle) which may interfere with or prevent everyday life functions but do not constitute a substantial disruption.

- **Congenital anomaly or birth defect**

- **Medically important event**

Medical judgment should be exercised in deciding whether SAE reporting is appropriate in other situations, such as important medical events that may not be immediately life-threatening or result in death or hospitalization but may jeopardize the participant or require medical or surgical intervention to prevent one of the other outcomes listed in the above definition. These events should usually be considered serious. Examples of such medical events include allergic bronchospasm requiring intensive treatment in an emergency room or at home, blood dyscrasias or convulsions that do not result in inpatient hospitalization, or the development of drug dependency or drug abuse.

8.11.3 Solicited Adverse Reactions

The term "reactogenicity" refers to the occurrence and intensity of selected signs and symptoms (ARs) occurring after IP injection. The eDiary will solicit daily participant reporting of ARs

using a structured checklist ([Section 8.9.4](#)). Participants will record such occurrences in an eDiary on the day of each IP injection and for the 6 days after the day of dosing.

Severity grading of reactogenicity will occur automatically based on participant entries into the eDiary according to the grading scales presented in [Table 5](#), which are modified from the Toxicity Grading Scale for Healthy Adult and Adolescent Volunteers Enrolled in Preventive Vaccine Clinical Trials ([DHHS 2007b](#)).

If a participant reported a solicited adverse reaction during the solicited period and did not record the event in the eDiary, the event should be recorded on the Reactogenicity page of the eCRF.

If the event starts during the solicited period, but continues beyond 7 days after dosing, the participants should notify the site to provide an end date and close out the event on the Reactogenicity page of the eCRF. If the participant reported an event after the solicited period (ie, after Day 7), it should be recorded as an AE on the AE page of the eCRF. All solicited ARs (local and systemic) will be considered causally related to dosing.

Table 5: Solicited Adverse Reactions and Grades

Reaction	Grade 0 (None)	Grade 1 (Mild)	Grade 2 (Moderate)	Grade 3 (Severe)	Grade 4 ¹ (Life-threatening)
Local					
Injection site pain	None	Does not interfere with activity	Repeated use of over-the-counter pain reliever > 24 hours or interferes with activity	Any use of prescription pain reliever or prevents daily activity	Requires emergency room visit or hospitalization
Injection site erythema (redness)	< 25 mm/ < 2.5 cm	25-50 mm/ 2.5-5 cm	51-100 mm/ 5.1-10 cm	> 100 mm/ > 10 cm	Necrosis or exfoliative dermatitis
Injection site swelling/induration (hardness)	< 25 mm/ < 2.5 cm	25-50 mm/ 2.5-5 cm	51-100 mm/ 5.1-10 cm	> 100 mm/ > 10 cm	Necrosis
Axillary (underarm) swelling or tenderness ipsilateral to the side of injection	None	No interference with activity	Repeated use of over-the-counter pain reliever > 24 hours or some interference with activity	Any use of prescription pain reliever or prevents daily activity	Emergency room visit or hospitalization
Systemic					

Reaction	Grade 0 (None)	Grade 1 (Mild)	Grade 2 (Moderate)	Grade 3 (Severe)	Grade 4¹ (Life-threatening)
Headache	None	No interference with activity	Repeated use of over-the-counter pain reliever > 24 hours or some interference with activity	Significant; any use of prescription pain reliever or prevents daily activity	Requires emergency room visit or hospitalization
Fatigue	None	No interference with activity	Some interference with activity	Significant; prevents daily activity	Requires emergency room visit or hospitalization
Myalgia (muscle aches all over body)	None	No interference with activity	Some interference with activity	Significant; prevents daily activity	Requires emergency room visit or hospitalization
Arthralgia (joint aches in several joints)	None	No interference with activity	Some interference with activity	Significant; prevents daily activity	Requires emergency room visit or hospitalization
Nausea/vomiting	None	No interference with activity or 1-2 episodes/24 hours	Some interference with activity or > 2 episodes/24 hours	Prevents daily activity, requires outpatient intravenous hydration	Requires emergency room visit or hospitalization for hypotensive shock
Chills	None	No interference with activity	Some interference with activity not requiring medical intervention	Prevents daily activity and requires medical intervention	Requires emergency room visit or hospitalization
Fever (oral)	< 38.0°C < 100.4°F	38.0-38.4°C 100.4-101.1°F	38.5-38.9°C 101.2-102.0°F	39.0-40.0°C 102.1-104.0°F	> 40.0°C > 104.0°F

Grading of Grade 4 events will be determined per investigator and assessment is recorded on the reactogenicity event page in the electronic case report form.

Note: Events listed above but starting > 7 days post study injection will be recorded on the AE page of the eCRF.

Causality for each event will be determined per assessment by the investigator. Source: Guidance for Industry – Toxicity Grading Scale for Healthy Adult and Adolescent Volunteers Enrolled in Preventive Vaccine Clinical Trials (DHHS 2007b).

Any solicited AR that meets any of the following criteria must be entered into the participant’s source document and must also be recorded as an AE in the participant’s Reactogenicity eCRF page:

- Solicited local or systemic AR that results in a visit to a healthcare practitioner (HCP; MAAE)
- Solicited local or systemic AR leading to the participant withdrawing from the study or the participant being withdrawn from the study by the investigator (AE leading to withdrawal)
- Solicited local or systemic AR continuing beyond 7 days post injection
- Solicited local or systemic AR that leads to participant withdrawal from IP
- Solicited local or systemic AR that otherwise meets the definition of an SAE

8.11.4 Medically Attended Adverse Events

An MAAE is an AE that leads to an unplanned visit to a HCP for medical evaluation (examinations/testing) and/or treatment that is not required per study protocol. The visit may be with an HCP at the clinical trial site or at another facility (eg, medical office, urgent care, emergency room). Investigators will review all AEs for the occurrence of MAAEs.

In addition, all RT-PCR–confirmed influenza and RT-PCR–confirmed symptomatic COVID-19 infections will be recorded as MAAEs and reported on the participant’s AE eCRF from Day 1 through the EoS.

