8.6 Physical Examination and Vital Signs

A full physical examination, including height and weight, will be performed at the Screening Visit; symptom-directed physical examinations may be performed at other clinic visits. Interim physical examinations will be performed at the discretion of the investigator. Any clinically significant finding identified by a healthcare professional during clinic visits should be reported as an MAAE ([Section 8.11.4](#)).

Vital sign measurements include the assessment of systolic and diastolic blood pressures, heart rate, respiratory rate, and body temperature. The preferred route of temperature assessment is oral. On the day of vaccination, vital signs will be collected once prior to vaccination and once

30 minutes after vaccination. Vital signs may be collected at other clinic visits in conjunction with a symptom-directed physical examination.

The information collected will be recorded in the eCRF.

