8.9.2 Assessments for Respiratory Viral Infections

The NP swab specimen(s) for pathogens, including influenza virus and SARS-CoV-2, will be collected any time from Day 1 to Day 361 (Month 12)/EoS if participants have protocol-defined ILI or symptoms suggestive of COVID-19 or other upper or lower respiratory infection, as defined in the ILI Case Definitions ([Section 8.11.5](#)). If participants experience these signs or symptoms, they will be instructed to contact the clinic to have an NP swab collected for testing. Nasopharyngeal swabs may be collected as part of a home visit in lieu of a clinic visit. In the event that NP swabs during ILI cannot be collected, any available influenza and/or SARS-CoV-2 testing results performed outside of the study should be captured.

Symptoms reporting for ILI will be conducted between Day 1 through Day 361 (Month 12)/EoS as described in [Section 8.9.4](#).

All RT-PCR-confirmed influenza ([Section 8.11.5](#)) and RT-PCR-confirmed symptomatic COVID-19 infections will be recorded as MAAEs along with relevant concomitant medications, hospitalizations, outpatient medical care, and details about severity, seriousness, and outcome. Asymptomatic RT-PCR-confirmed COVID-19 infections are not to be recorded as MAAEs.

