8.11.5 Influenza-like Illness Case Definitions

Protocol-defined ILI

A protocol-defined ILI is determined by the occurrence of at least 1 respiratory illness symptom concurrently with at least 1 systemic symptom, or the occurrence of any 2 or more respiratory symptoms, as shown in [Table 6](#).

Table 6: Respiratory and Systemic Symptoms for Protocol-defined Influenza-like Illness

Respiratory symptoms	Systemic symptoms
1. Sore throat	1. Body temperature > 37.2°C [> 99°F]
2. Cough/rhinorrhea/nasal congestion (≥1 of the 3 symptoms count as 1 respiratory symptom)	2. Chills
3. Sputum production	3. Tiredness
4. Wheezing	4. Headache
	5. Myalgia
	6. Nausea/vomiting

Respiratory symptoms	Systemic symptoms
5. Difficulty breathing	7. Diarrhea

CDC-defined ILI

A CDC-defined ILI is defined as body temperature $\geq 37.8^{\circ}\text{C}$ (100°F) accompanied by cough and/or sore throat.

RT-PCR-confirmed Protocol-defined Influenza Infection

An RT-PCR-confirmed protocol-defined influenza infection is defined as a positive influenza result on a respiratory sample by RT-PCR performed at the Global Central Laboratory and/or a local certified laboratory within 7 days of onset of protocol-defined ILI symptoms at any time during the study period.

RT-PCR–confirmed CDC-defined Influenza Infection

An RT-PCR–confirmed CDC-defined influenza infection is defined as a positive influenza result on a respiratory sample by RT-PCR performed at Global Central Laboratory and/or a local certified laboratory within 7 days of onset of CDC-defined ILI symptoms at any time during the study period.

Through Day 28, any illness assessed for protocol-defined ILI/suspected SARS-CoV-2 and reports of asymptomatic RT-PCR–confirmed COVID-19 events should be captured as an AE in the AE eCRF. Starting on Day 29, asymptomatic COVID-19 events should no longer be captured as AEs, and illnesses assessed for protocol-defined ILI/suspected SARS-CoV-2 should only be captured as AEs if they have RT-PCR–confirmed influenza or RT-PCR–confirmed symptomatic COVID-19 infections (must be recorded as MAAEs), or if they otherwise meet the criteria for reporting as an SAE ([Section 8.11.2](#)), MAAE ([Section 8.11.4](#)), or event leading to discontinuation from the study. An event should not be recorded as an MAAE based on visits to the clinical trial site for protocol-required assessment of ILI symptoms and NP swab collection.

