6.6.2.1 Overview of Unsolicited TEAEs

An overall summary of unsolicited TEAEs up to 28 days after IP injection (or other time frames, as applicable) including the number and percentage of participants who experienced the following will be presented:

- Any unsolicited TEAEs
- Any unsolicited treatment-related TEAEs
- Any serious TEAEs
- Any treatment-related serious TEAEs
- Any unsolicited severe TEAEs
- Any unsolicited treatment-related severe TEAEs
- Any unsolicited medically attended TEAEs
- Any unsolicited treatment-related medically attended TEAEs
- Any unsolicited treatment emergent AESI
- Any unsolicited TEAEs leading to discontinuation from participation in the study.

Listings containing individual participant AE data for unsolicited AEs, unsolicited AEs leading to discontinuation from participation in the study, SAEs, AESI, MAAEs will be provided separately.

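### Recording every RT-PCR-confirmed influenza and symptomatic COVID-19 case as an MAAE mixes the relative-efficacy result into the any-MAAE row; a supplementary row should separate the cases recorded only by that rule

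*Protocol*

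**What the plan says.** Protocol 8.11.4 opens with a definition based on seeking care: "An MAAE is an AE that leads to an unplanned visit to a HCP for medical evaluation", or for treatment, where the protocol does not itself require the visit. The next paragraph adds a second route: "In addition, all RT-PCR–confirmed influenza and RT-PCR–confirmed symptomatic COVID-19 infections will be recorded as MAAEs". That route runs from Day 1 to end of study and carries no condition that anyone sought care.

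The rule is repeated. Protocol 8.9.2 has "symptomatic COVID-19 infections will be recorded as MAAEs along with relevant concomitant medications, hospitalizations, outpatient medical care", and 8.11.5 makes it mandatory from Day 29. Section 8.11.5 also limits the first route: "An event should not be recorded as an MAAE based on visits to the clinical trial site for protocol-required assessment of ILI symptoms". Section 8.6 points the other way for examination findings: "Any clinically significant finding identified by a healthcare professional during clinic visits should be reported as an MAAE".

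MAAE frequency to Day 361/end of study is part of a primary safety endpoint (protocol Section 3, SAP 3.1). SAP 6.6.2.1 and 6.6.2.2 list "Any unsolicited medically attended TEAEs" among the summaries, by system organ class and preferred term in 6.6.2.2, together with treatment-related MAAEs. SAP 6.6.2 extends the MAAE summaries to 180 days and to Day 361/end of study. It defines an MAAE by a visit that may be either scheduled or unscheduled, and it does not mention the RT-PCR rule.

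**The concern.** Cases are found by active surveillance: a weekly symptom diary, contact by the investigator, and a swab that may be taken at home (protocol 4.1 and 8.9.2). Under protocol Table 6, a runny nose with tiredness is enough for protocol-defined ILI. A participant can therefore be confirmed positive without having sought care and still count as an MAAE.

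Every secondary efficacy event is RT-PCR-confirmed influenza, so every efficacy event also enters the MAAE count. If the vaccines differ in efficacy, the any-MAAE comparison carries that difference. Better efficacy of mRNA-1010 could offset an excess of other MAAEs, and worse efficacy could look like a safety signal. A reader of the row cannot tell which part reflects care-seeking.

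**Working it through.** The plan states no MAAE rate, influenza attack rate, COVID-19 rate or care-seeking rate, so there is no figure to reproduce. Apart from the arm size of about 3000 (protocol 9.3), every rate below is an assumption that shows direction and range.

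**1. How many counted MAAEs might be rule-only.** Let g be other MAAEs, f confirmed influenza, c confirmed symptomatic COVID-19 and s the share of those infections with non-protocol care, treated as non-overlapping.

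- Counted rate = g + f + c
- Care-seeking rate = g + s(f + c)
- Rule-only rate = (1 − s)(f + c)

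Middle case (g 10%, f 3%, c 5%, s 50%): counted 18.0%, care-seeking 14.0%. The difference of 4.0% is 120 of 3000, and 4.0/18.0 = 22% of counted MAAEs. Over g 5–20%, f 1–5%, c 2–10% and s 20–80%, the rule-only number runs from 18 to 360 per arm, or about 3% to 60% of counted MAAEs.

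**2. Infections equally frequent in both arms.** Take true MAAE rates of 13% and 10%, add a rate r of infections to each arm independently, and assume that none led to care (an upper bound on dilution). Counted rate = 1 − (1 − true rate)(1 − r).

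| r | mRNA-1010 | Comparator | Ratio | Difference (points) |
|---|---|---|---|---|
| 0 | 13.0% | 10.0% | 1.30 | 3.0 |
| 3% | 15.6% | 12.7% | 1.23 | 2.9 |
| 6% | 18.2% | 15.4% | 1.18 | 2.8 |
| 10% | 21.7% | 19.0% | 1.14 | 2.7 |

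The ratio shrinks visibly. The absolute difference is 3.0 × (1 − r) and hardly moves.

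**3. Influenza that differs by arm.** Let d be the true excess of other MAAEs on mRNA-1010, f the comparator influenza rate and rVE the relative efficacy, over one common window. Influenza contributes f(1 − rVE) − f = −f × rVE.

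- Counted difference = d − f × rVE
- Difference if only attended influenza counts = d − s × f × rVE

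With d = 1.0 point, f = 3% and s = 30%:

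| rVE | Counted difference | Attended influenza only |
|---|---|---|
| +30% | 1.0 − 0.9 = +0.1 | 1.0 − 0.27 = +0.73 |
| 0 | +1.0 | +1.0 |
| −30% | 1.0 + 0.9 = +1.9 | 1.0 + 0.27 = +1.27 |

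A non-zero relative efficacy is thus the main way the absolute difference moves. Removing rule-only cases reduces the shift but does not abolish it, because attended influenza is a genuine MAAE and stays in. A count without any confirmed influenza returns d.

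**4. Whether planned output already gives this count.** Tables by preferred term show influenza and COVID-19 terms but not whether care was sought. One participant can contribute to several terms, so the number with any MAAE apart from rule-only infections cannot be obtained by subtracting rows.

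**The case against.** The rule is open, consistent across three protocol sections and has a purpose. From Day 29, illnesses assessed for ILI or COVID-19 are captured as AEs only if confirmed by RT-PCR or otherwise reportable, so the rule ensures that confirmed infections are recorded. MAAEs are descriptive: protocol Table 8 gives counts and percentages without confidence intervals, and SAP 6.5 places them outside the controlled testing. The tables by preferred term expose the infections, treatment-related MAAEs have their own rows, an MAAE listing is planned, and confirmed influenza is reported by arm in the efficacy analyses. The overview in SAP 6.6.2.1 is mainly a 28-day table, when few infections will have accrued. All of this stands. It confines the problem to the any-MAAE row, chiefly over the longer windows, and rules out calling the rule an error.

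A reader might infer three stronger things. The first is that efficacy cases went without medical care; the documents say only that the count does not depend on care. The second is that a diluted ratio distorts a planned result; no MAAE ratio is planned, and the absolute difference in step 2 moves from 3.0 only to 2.7–2.9 points. The third is that findings reported under protocol 8.6 should become ordinary AEs. Unsolicited AEs are collected for only 28 days, so non-serious findings at the Day 181 and Day 361 clinic visits could then be lost.

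The objection does not supply the missing count. Nor does it answer step 3, where the absolute difference itself shifts.

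**Conclusion.** The point holds as a limit on interpretation with an inexpensive remedy. The any-MAAE row combines events for which care was sought, infections recorded by rule, and the relative-efficacy result. Its size cannot be derived from the documents; the figures above rest on assumed attack, care-seeking and efficacy rates. If relative efficacy is zero, influenza causes dilution only. If it is not, the absolute difference shifts by f × rVE, which is 0.9 point at 3% and 30%.

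The two MAAE definitions also need attention. Protocol 8.11.4 requires an unplanned visit outside the protocol, while SAP 6.6.2 admits scheduled visits. SAP Section 1 gives the SAP precedence where methods differ, and SAP Section 7 declares no changes. Under the SAP's wording, a clinic swab visit could itself count as attendance, which protocol 8.11.5 excludes.

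**What to change.** Keep the recording rule and all planned MAAE tables. In the SAP 6.6.2.1 and 6.6.2.2 MAAE summaries, above all those to Day 180 and Day 361/end of study:

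- Add a supplementary row for participants with any MAAE other than an infection recorded only under the RT-PCR rule. A participant with another MAAE stays in this row.
- Add a separate row for the rule-only infections.
- Derive attendance from the outpatient, emergency, telemedicine and hospitalisation fields already collected (protocol 8.17.2 and Schedule of Events footnote 23), without counting protocol-required ILI visits.
- Section 8.17.2 collects outpatient use only when the information can be obtained, so an empty field does not prove that no visit took place. State how missing attendance is handled, or also show the row without any RT-PCR-confirmed influenza or COVID-19. That version needs no attendance data and removes the efficacy contribution entirely.
- Reconcile the MAAE definition in SAP 6.6.2 with protocol 8.11.4, and state how protocol 8.6 fits with 8.11.4, without moving 8.6 findings out of collection after Day 28.

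The cost is one derived flag, one to three table rows and a wording change, with no new data collection. The downsides are slightly longer safety tables and some misclassification of attendance.
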